### **5.3 Dose Proportionality**

For the dose cohorts Up to 3 mg/m^2, 6 mg/m^2, 10 mg/m^2, and 13 mg/m^2, a dose proportionality regression assessment for log-transformed  $C_{max}$ ,  $AUC_{0-last}$ , and  $AUC_{0-inf}$  and log-transformed dose will be analyzed using a power model:  $\ln(\text{PK parameter}) = \mu + \beta \times \ln(\text{dose})$  will be conducted for the free tretinoin and liposome encapsulated tretinoin. The 90% confidence intervals (CI) around the slopes ( $\beta$ ) from each of these regression analyses will be obtained from the model and presented. Plots of the log-PK parameter by log-dose ( $AUC_{last}$ ,  $AUC_{inf}$ , and  $C_{max}$ ) will be produced for the dose cohorts for the PK Population.

## **6 Safety analysis**

All summaries of safety data will be based on the Safety Population. Adverse events, 12-lead ECGs, vital signs (BP, respiratory rate, pulse rate, and oral body temperature), and safety laboratory (hematology, clinical chemistry, coagulation, and urinalysis) data will be reviewed and summarized on an ongoing basis during the study to evaluate the safety of subjects. Any clinical laboratory, ECG, BP, respiration, or pulse rate abnormalities of potential clinical concern will be described.

Medical history and physical examination information, as applicable, collected during the study will be captured for inclusion into the study database, unless otherwise noted. Any untoward findings identified on physical examination conducted after the administration of the first dose of study drug will be captured as an AE, if those findings meet the definition of an adverse event. Data collected at screening will be included in the study database. Physical examination (PE) will be performed at the visits as indicated in [Table 2](#) above. The assessment should include, but not be limited to, the following body systems: general appearance and evaluation of dermatological system, head, eyes, ears/nose/throat, neck, lymph nodes, lungs, heart, abdomen, neurological, skin and musculoskeletal system. An abbreviated PE will include: heart, lungs, abdomen, skin and neuromuscular system. A symptom-directed PE may be performed at any time.

Safety evaluations will be based on the incidence, severity, and relatedness (Related, Probably Related, Probably Not Related, Not Related) of AEs and changes in subjects' physical examination findings, ECGs, vital signs, and clinical laboratory results. In the analysis of change from baseline for clinical laboratory parameters, 12 lead ECGs, and vital sign parameters, baseline is defined as the last value on or before the first dose of study drug.

## **6.1 Study product exposure**

Exposure to study drug will be listed by subject and treatment, indicating dose date and time. Any deviations will be documented.

## **6.2 Adverse Events**

All AEs (serious and non-serious) will be collected from the start of signing the ICF and until 30 days after the administration of the study drug. All reported AEs will be coded using Medical Dictionary for Regulatory Activities Version 24.0 or higher. All AEs will be graded using National Cancer Institute Common Terminology Criteria for Adverse Events (NCI CTCAE v5.0) refer to the protocol for further information. The causal relationship to study drug will be specified as Related, Probably Related, Probably not related, Not Related. For serious adverse events (SAE) that occur at any time following post dosing or end of the study and there is a reasonable possibility that the SAE is related to the study drug by the Investigator it must be promptly reported to the Sponsor. The incidence of treatment-emergent AEs (TEAE) – events with onset dates on or after the first dose date of the study drug and up to 30 days following the last dose of study drug – will be included in incidence tables. Events with missing onset dates will be considered treatment-emergent. All AEs will be summarized by severity and by relationship to study treatment. If a subject experiences more than 1 occurrence of the same AE (preferred term), the occurrence with the greatest severity and with association (Relationship to study treatment = ‘Related’ or ‘Probably Related’) to the study treatment will be used in the summary tables. Serious adverse events and AEs causing discontinuation will be tabulated. Treatment related SAEs and AEs causing discontinuation will also be summarized. All deaths during the study will be summarized and listed. All AEs will be listed by subject, System Organ Class (SOC) and Preferred Term (PT), along with information regarding onset, duration, CTCAE grade v5, and relationship to study treatment, action taken with study treatment, nature of event, and outcome. (Refer to the protocol for further information.) All tabulations will be presented by treatment. All AEs will be listed by subject and by treatment.

The injection site assessments will be assessed using a visual irritation scale (0-7): 0 = no evidence of irritation, 1 = minimal erythema, barely perceptible, 2 = definite erythema, readily visible; minimal edema or minimal papular response, 3 = erythema and papules, 4 = definite edema, 5 = erythema, edema and papules, 6 = vesicular eruption, or 7 = strong reaction spreading beyond application site. These will be listed along with other AEs and will be listed separately.

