8 INVESTIGATIONAL PLAN

8.1 Overall Study Design

Up 32 subjects, comprised of up to 4 cohorts of 8 subjects each, will receive a single IV dose of study drug. Six of the 8 subjects in each cohort will receive HF1K16 and 2 subjects will receive placebo in a blinded manner.

Planned treatments are:

- Cohort 1: up to 3 mg/m² of HF1K16 or placebo
- Cohort 2: up to 6 mg/m² of HF1K16 or placebo
- Cohort 3: up to 10 mg/m² of HF1K16 or placebo
- Cohort 4: up to 13 mg/m² of HF1K16 or placebo

The duration of study participation for all subjects is up to approximately 38 days, including a screening period of up to 28 days.

After providing written informed consent, subjects will undergo screening for eligibility. Eligible subjects will be admitted to the Clinical Research Unit (CRU) on Day -1, one day prior to dosing, remain at the CRU for 3 overnight stays, and be discharged the morning of Day 3, approximately 48 hours post-dose. Subjects will have a follow-up telephone call on Day 8 ± 2 days to collect AE and concomitant medication information.

Safety assessments will include monitoring of AEs, vital signs (blood pressure, pulse rate, respiration rate, oral temperature), clinical laboratory findings, resting 12-lead ECGs, physical examination findings, including skin assessment, and injection site assessments. Vital sign assessments will be done at screening, pre-dose and 0.25, 0.5, 0.75, 1, 1.5, 2, 6, 24 and 48 hours post-dose relative to the start of infusion. Clinical safety laboratory assessments will be performed at screening, on Day -1 and Day 3. A resting 12-lead ECG will be completed at screening, Day -1 and 12, 24 and 48 hours post-dose. A full physical examination will be conducted at screening, and abbreviated physical examinations will be conducted on Day -1 and Day 3. Injection site assessments will be performed prior to and at 4 and 24 hours relative to the start of infusion. Subjects will be discontinued in the event of any AE that may jeopardize the subject's safety and wellbeing.

Safety and tolerability data collected up to Day 8 ± 2 days for each cohort, and PK data, will be evaluated prior to proceeding to the next higher dose cohort. Administration of the next higher dose to a new cohort of subjects will be permitted only if adequate safety, and tolerability data have been demonstrated.

See [Table 1](#) for the details and the timing and scheduling of all study procedures.

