13.2 Adverse Events

Adverse events will be recorded beginning immediately after the Informed Consent Form (ICF) is signed. Subjects will be instructed to report AEs during the study and staff will query subjects regarding AEs throughout the study. The Investigator (and/or designee) must document all AEs reported by the subject from the time subjects give consent through the follow-up/completion visit. Any subject who is withdrawn from the study due to an AE shall be followed until the event has resolved or stabilized, and the Investigator will document available follow-up information on the subject's source documentation and eCRF.

13.2.1 *Definitions of Adverse Events*

An AE is any unfavorable and unintended sign, symptom, or disease temporally associated with the use of medicinal (investigational) product, whether or not related to the medicinal (investigational) product. An AE is any symptom, sign, illness, or experience that develops or

worsens in severity during the course of the study. Adverse events reported after consent but before the first dose of study drug are still to be documented by the Investigator but will be considered non-treatment-emergent AEs. Adverse events will be considered treatment-emergent if the onset date is after the first dose of study drug. The severity of each AE will be graded by the Investigator using the National Cancer Institute (NCI) CTCAE v5.0 as follows:

- **Grade 1:** Mild; asymptomatic or mild symptoms; clinical or diagnostic observations only; intervention not indicated;
- **Grade 2:** Moderate; minimal, local, or noninvasive intervention indicated; limiting age appropriate instrumental activities of daily living (ADL);
- **Grade 3:** Severe or medically significant but not immediately life-threatening; hospitalization or prolongation of hospitalization indicated; disabling; limiting self-care ADL;
- **Grade 4:** Life-threatening consequences; urgent intervention indicated;
- **Grade 5:** Death related to AE.

Abnormal results of laboratory tests or diagnostic procedures are considered AEs if the abnormality:

- Is associated with clinical signs or symptoms
- Is considered by the Investigator to be of clinical significance
- Results in study withdrawal
- Fulfills any of the criteria for a serious AE (SAE), as described in this section
- Requires treatment

An SAE is any untoward medical occurrence at any dose that:

- Results in death
- Is life threatening

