13.2.2 Recording Adverse Events

All AEs (regardless of seriousness or relationship to study drug) including those from the time of consent to the follow-up/completion visit are to be recorded in the subjects’ source documents and on the corresponding page(s) in the eCRF. Whenever possible, symptoms, signs, and laboratory abnormalities should be grouped as a single syndrome or diagnosis. The Investigator should specify the date of onset, severity, action taken with respect to study drug, corrective treatment/therapy given, outcome and his/her opinion as to whether there is a reasonable possibility that the AE was caused by the study drug, according to the definitions noted. All medications administered to treat an AE must be recorded in the subject’s source documentation and documented in the eCRF.

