**Table 1 Dose Escalation**

Cohort (single infusion dosing)	Dose (mg/ m  ) Once
1	Up to 3 mg/m  (6 HF1K16 and 2 placebo)
2	Up to 6 mg/m  (6 HF1K16 and 2 placebo)
3	Up to 10 mg/m  (6 HF1K16 and 2 placebo)
4	Up to 13 mg/m  (6 HF1K16 and 2 placebo)

*Note: the 'Up to...' will be removed and the final dose replaced in the TLF Shells..*

Refer to the dosing escalation stopping rules (refer to the protocol for the complete description).

This study will include an up to 28-day screening period (Days -28 to -1), including a clinic check-in (Day -1), a treatment day (Day 1), and observation period refer to [Table 2](#) below. Subjects will exit from the study after completing Follow-up telephone call on Day 8 ( $\pm$  2 days) or early withdrawal evaluation(s). The expected duration of participation for each subject, therefore, will be approximately 38 days.

Eligible subjects will be admitted to the clinic on Day -1 for baseline evaluations. Safety assessments including physical examination, vital signs, ECGs (triplicate for specific time points), and standard clinical laboratory evaluations will be performed, and following enrollment, the subjects will be randomized. Subjects will be administered the study drug on Day 1, monitored according to the Schedule of Procedures [Table 2](#) below during in-clinic confinement, and followed up during outpatient visits. Blood samples for PK analysis will be collected pre-dose and through post-dose (Day 8 ( $\pm$  2 days)).

Refer to [Table 2](#) for the Schedule of Procedures.

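### SAP 6.2 says all AEs are collected, and TEAEs counted, to 30 days after dosing, but the last scheduled AE query is the Day 8 ±2 call; its date-only start rule is a second, small defect

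*SAP*

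**What the plan says.** **Collection period.** SAP 6.2 says that all AEs "will be collected from the start of signing the ICF and until 30 days after the administration of the study drug". The incidence tables then take TEAEs with onset from the first dose date "and up to 30 days following the last dose of study drug".

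**Scheduled contact.** Protocol 8.1: "Subjects will have a follow-up telephone call on Day 8 ± 2 days to collect AE and concomitant medication information". Protocol 13.2 requires the Investigator to "document all AEs reported by the subject from the time subjects give consent through the follow-up/completion visit", and Protocol 13.2.2 says of all AEs, "including those from the time of consent to the follow-up/completion visit are to be recorded". In SAP section 3, below Table 1: "Subjects will exit from the study after completing Follow-up telephone call on Day 8" (±2 days), or after early-withdrawal evaluations, with participation of about 38 days.

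**Start of the TEAE window.** SAP 6.2 uses the calendar date of the first dose and treats a missing onset date as treatment-emergent. Protocol 13.2.1 classes AEs reported before the first dose as not treatment-emergent, and then says: "Adverse events will be considered treatment-emergent if the onset date is after the first dose of study drug".

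**Declared changes.** Protocol section 14 expects the SAP to set out any changes from the protocol's analyses. SAP section 9 declares none.

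**The concern.** AE incidence is the first primary endpoint listed in SAP 2.3, and this is the first study of HF1K16 in humans. A reader who takes SAP 6.2 at its word will treat the TEAE tables as resting on 30 days of collection. If active questioning ends after 5 to 9 days, the absence of later events in the tables says much less than that window implies. The few late events that do appear will have been reported selectively.

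The start rule raises a second, smaller question. The infusion begins at about 8 a.m. on Day 1 (Protocol 11.3). An AE that starts earlier that morning cannot be caused by the drug, yet under SAP 6.2 it counts as treatment-emergent.

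**Working it through.** **1. The plan's own duration.** Inputs: screening of up to 28 days, and a call on Day 8 ±2, so Day 10 at the latest (Protocol 8.1, SAP section 3).
28 + 10 = 38 days. This reproduces the stated participation exactly, so the plan's own timeline ends at the call.

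**2. What 30-day scheduled collection would need.** Dosing is on Day 1, so 30 days after dosing is Day 31.
28 + 31 = 59 days, against the stated 38.

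**3. The part of the window with no scheduled query.** Days from dosing to call = call day − 1.

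| Call on | Days after dosing | Days left of 30 | Share of window |
|---|---|---|---|
| Day 6 | 5 | 25 | 83% |
| Day 8 | 7 | 23 | 77% |
| Day 10 | 9 | 21 | 70% |

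These are shares of calendar time. They do not estimate the share of events missed, which the documents give no means to calculate.

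**4. Routes by which a later event could still be recorded.**
- Spontaneous report by the subject.
- An SAE brought to the Investigator's attention within 30 days and judged drug-caused (Protocol 13.2.4).
- Conditional follow-up of something already known: contacts after discontinuation for an AE (9.4), repeat liver tests (10.6), repeat tests for unresolved laboratory abnormalities (13.1.5), and following an AE to resolution or stabilization (13.2.4).

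None of these is a scheduled query for new AEs in all subjects.

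**5. Where the protocol's own period ends.** Protocol 13.2 and 13.2.2 end at the follow-up/completion visit. The footnotes to Protocol Table 1 and SAP Table 2 call Day 3 the completion visit, while Protocol 8.1 gives the Day 8 ±2 call the task of collecting AEs. The call is the sensible reading, but the term is ambiguous. Neither reading reaches 30 days.

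**6. Start rule.** Day 1 before infusion runs from midnight to about 8 a.m., about 8 hours. As a share of the period from midnight on Day 1 to the call:
- call on Day 6: 8 / (8 + 5 × 24) = 6.2%
- call on Day 10: 8 / (8 + 9 × 24) = 3.6%

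For scale only, assume a constant hazard and a 30-day AE probability p, which the documents do not give. Expected subjects of 32 with onset in those 8 hours = 32 × [1 − (1 − p)^((8/24)/30)]. This gives 0.04 at p = 10%, 0.13 at 30% and 0.25 at 50%. If one subject were misclassified, an active cohort would move by 1/6 (17 points), or pooled placebo (4 × 2 = 8 subjects) by 1/8 (12.5 points).

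The protocol's sentence is not clean either. Read strictly by date, onset after the first dose would exclude every Day 1 event, including reactions during the infusion.

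**The case against.** **The 30-day limit is only an inclusion rule.** This is largely right for the TEAE definition. The SAP does not claim complete ascertainment to 30 days, and counting a late event that happens to be reported is not in itself an error, since the TEAE sentence in Protocol 13.2.1 has no upper limit. It does not rescue the preceding sentence in SAP 6.2, which says that all AEs are collected for 30 days.

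**Follow-up does continue after the call.** It can, by the routes in step 4, so a reader should not infer that later events are unobservable or enter only as spontaneous reports and related SAEs. But those routes are conditional or unsolicited. SAP section 3 also mentions outpatient visits, yet the only contact scheduled after discharge on Day 3 is the telephone call.

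**Few events would be lost after one 60-minute infusion.** This is plausible, because acute reactions would cluster early. It is why the 70% to 83% must not be read as lost events or as bias. Any figure for missed late events would need an assumed reporting rate that the documents do not supply.

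**The SAP's start rule is conservative.** It can only overcount, it does so equally in all arms, and it avoids losing all Day 1 events under a strict reading of the protocol. All of that stands. What remains is a conflict with the protocol's explicit rule for pre-dose AEs. Protocol 13.2.2 asks for the date of onset. Whether the eCRF also holds a time or a pre-dose/post-dose flag cannot be seen.

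**Conclusion.** The SAP states a 30-day collection period that the design does not have. Scheduled AE ascertainment ends 5 to 9 days after dosing, leaving 21 to 25 of 30 days without a planned query. This follows from the documents' own dates and needs no assumption beyond taking the call as the last scheduled AE contact, which the 38-day duration confirms.

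The consequence is limited to the accuracy of the reported safety window. A reader might infer bias between arms or unsafe escalation, and the documents support neither. Follow-up is the same in every arm, escalation uses data through Day 8 (Protocol 10.6), and the safety analysis is descriptive (Protocol 14.7), so no error rate or sample size changes.

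The start rule is a real but small error. It concerns about 8 hours, can only overcount, and matters mainly because one subject is a large fraction of a cohort of six.

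The point is worth correcting because the endpoint is primary and the correction is cheap.

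**What to change.** 1. In SAP 6.2, state that AEs are collected from consent through the Day 8 ±2 call, or through the early-withdrawal evaluation or last contact where there is no call. State in both documents that the follow-up/completion visit means this call for AE collection, since Day 3 is also called the completion visit.
2. Footnote the AE tables to say that systematic ascertainment ended at that contact. Flag, or list separately, any event with later onset.
3. Define TEAE as onset or worsening at or after the start of infusion. For Day 1 events, compare onset time or a pre-dose/post-dose flag with the infusion start time already recorded under Protocol 10.3. Count unknown times as treatment-emergent, in line with the SAP's rule for missing dates. This also settles the ambiguous protocol sentence.
4. Record in SAP section 9 any difference from the protocol that remains, such as a 30-day upper limit if one is kept. Reconcile the reporting period for drug-related SAEs, which is 30 days in Protocol 13.2.4 and has no time limit in SAP 6.2.

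**Cost.** Wording in SAP 6.2 and section 9, a clarification in the protocol, one footnote and one flag for late onset. A Day 1 onset time or flag must be added if the eCRF lacks it. The stated follow-up becomes shorter. No visit, subject or analysis is added.

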9.3 Prohibitions and Restrictions

Subjects must be willing to adhere to the following prohibitions and restrictions until the end of the study (follow-up telephone call):

- No consumption of alcohol or food containing alcohol from 48 hours prior to Day -1 until the end of study.
- No excessive exercise from 48 hours prior to Day -1 until the end of study.

- No consumption of foods or drinks containing caffeine from 48 hours prior to Day -1 until the end of study.
- No administration of any prescription drugs within 14 days prior to first dose of study drug until the end of study.

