### 2.3 Primary endpoints

- Incidence of Adverse Events (AEs) and Serious Adverse Events (SAEs)
- Injection Site Assessments

- Physical examination
- Laboratory abnormalities (hematology, serum chemistry, and urinalysis)
- Vital signs (blood pressure, respiratory rate, pulse rate, and oral body temperature)
- 12-lead electrocardiogram (ECG)

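### Treatment-emergence is decided by onset alone, so an AE that begins before Day 1 and worsens after the infusion can be missing from the SAP's TEAE incidence tables

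*SAP*

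**What the plan says.** SAP 6.2 puts treatment-emergent AEs in the incidence tables. It defines them as "events with onset dates on or after the first dose date of the study drug", with an upper limit of 30 days after the last dose. Its one supplementary rule concerns missing data: "Events with missing onset dates will be considered treatment-emergent".

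Protocol 13.2.1 also uses onset: "Adverse events will be considered treatment-emergent if the onset date is after the first dose of study drug". It says that AEs reported between consent and the first dose are to be documented, "but will be considered non-treatment-emergent AEs".

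The same protocol section defines an AE broadly. It covers a symptom, sign or illness that newly develops and also one that "worsens in severity during the course of the study".

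Protocol 13.2.2 lists what the investigator records for each AE, including date of onset and severity. It does not say how to record a change of grade. SAP 2.3 lists the incidence of AEs and SAEs first among the primary endpoints.

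**The concern.** In the protocol, worsening is enough to make something an AE, but worsening cannot make an AE that is already open at dosing treatment-emergent. Suppose a Grade 1 event begins during screening and becomes Grade 2 after the infusion. If the site keeps one record and updates the grade, the event keeps its pre-dose onset date and fails the TEAE rule. The post-infusion part, which is what a single-dose safety study wants to count, then has no place in the TEAE incidence tables.

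Pre-dose AEs are plausible here. AEs are collected from consent, screening can last 28 days, and some restrictions start before dosing, for example "No consumption of foods or drinks containing caffeine from 48 hours prior to Day -1 until the end of study". Protocol 6.4 also names skin as a potential target organ to be monitored, so a minor skin event that is present before dosing and worse afterwards would be of direct interest.

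At stake is whether the tables that report incidence by treatment include every subject whose condition deteriorated after the infusion. With 6 active subjects per dose, a single subject is visible in the percentages.

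**Working it through.** The plan states no figure to reproduce; SAP 3.1 says that no formal sample size calculation was made. The check is a reading of the rules followed by simple arithmetic for scale.

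**Step 1. Apply the two rules to each type of event**

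| Event | SAP 6.2 (date rule) | Protocol 13.2.1 |
|---|---|---|
| Starts after the infusion begins | TEAE | TEAE |
| Starts on Day 1 before the infusion | TEAE, because the date equals the first dose date | Not a TEAE |
| Starts after consent and before Day 1, no change after dosing | Not a TEAE | Not a TEAE |
| Starts after consent and before Day 1, grade rises after dosing, one record kept | Not a TEAE | Not a TEAE |
| Same, but a new record is opened at the worsening | TEAE | TEAE |
| Onset date missing | TEAE | Not addressed |

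Rows 4 and 5 describe the same clinical course with opposite classification, and no visible text tells the site which record to make. Row 2 shows that the documents also disagree with each other on Day 1. Under the SAP, the gap is limited to onsets dated before Day 1.

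**Step 2. Where the row 4 event still appears**

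- SAP 6.2: the listing of all AEs, and the summaries by severity and relationship, which are worded for all AEs.
- Protocol 14.7: the system organ class and preferred term tables, which are worded for AEs without a TEAE restriction.
- Protocol 10.6 and 10.7: the stopping criteria use AE grade, and the Safety Monitoring Committee reviews AEs. Neither refers to treatment-emergence.

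The loss is therefore confined to the SAP's TEAE incidence tables.

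**Step 3. Size of one omitted subject**

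Inputs, from Protocol 8.1 and the Synopsis: 6 active and 2 placebo per cohort, and up to 4 cohorts. That gives 4 × 6 = 24 active and 4 × 2 = 8 placebo, with placebo pooled. The shift from one subject with no other TEAE is 1/n:

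- dose group: 1/6 = 16.7 points
- all active: 1/24 = 4.2 points
- pooled placebo: 1/8 = 12.5 points

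**Step 4. How often it might occur (assumption only)**

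The documents give no rate. Let q be the assumed chance that a subject has an AE with onset before Day 1 that rises in grade after dosing and is not re-recorded. The chance of at least one such subject among 24 active is 1 − (1 − q)^24:

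- q = 1%: 21%
- q = 2%: 38%
- q = 5%: 71%
- q = 10%: 92%

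This range is illustrative. It shows how the answer depends on q and does not estimate q.

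**The case against.** The strongest reply is that the AE definition already supplies the remedy. If worsening is itself an AE, a site may record it as a new AE with onset at the worsening, and the event then passes the TEAE rule. Other text is consistent with this. Protocol 13.1.5 has clinically significant out-of-range laboratory values after dosing recorded as AEs. SAP 6 captures post-dose examination findings that meet the AE definition. SAP 6.2 foresees several occurrences of the same preferred term. eCRF instructions and a data management plan (Protocol 18.1 and 18.3) are mentioned but not available here, and they may settle the matter. This stands in part: the omission depends on recording practice. But a site that keeps one record and updates its grade breaks no visible rule, so the outcome is left to chance.

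Three stronger readings are tempting, and the documents do not support them.

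- A reader might infer that the event drops out of the primary endpoint altogether. The endpoint is worded as incidence of AEs, not of TEAEs, and Step 2 shows several outputs that keep the event. Those outputs do not fully replace the TEAE tables, because an all-AE table mixes screening events with post-dose events and cannot show that a grade rose after the infusion.
- A reader might infer that the rule always makes the drug look safer. It lowers counts in placebo as well as active, so the contrast has no fixed direction. The neighbouring SAP rules on missing onset dates and on Day 1 onsets lean towards inclusion.
- A reader might assume that 5–20% of subjects have an AE ongoing at dosing and conclude that about 2 to 6 of 32 are misclassified (32 × 0.05 = 1.6; 32 × 0.20 = 6.4). That counts subjects with any ongoing AE under an assumed rate. Only those whose event then worsens and is not re-recorded are affected.

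**Conclusion.** The point holds in limited form. Both definitions rest on onset alone and neither provides for worsening. An AE that began before Day 1 and increased in grade after the infusion is left out of the SAP's TEAE incidence tables unless the site opens a new record.

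The effect on a group's TEAE count can only be downward. The sizes in Step 3 assume that the subject has no other TEAE; in a single system organ class or preferred term row, the condition is no other TEAE in that row. How many subjects would be affected cannot be derived from the documents.

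Nothing here shows a failure of dose escalation oversight, since the stopping criteria do not depend on TEAE status, and no formal safety test is planned. This is a defect in how a descriptive safety table is defined. It is worth correcting because the primary objective is safety and the groups are small. The Day 1 disagreement between the documents is a second reason to rewrite the same sentence.

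**What to change.** Make three changes, before unblinding so that the rule is not post hoc:

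1. In SAP 6.2 and Protocol 13.2.1, use one definition: a TEAE is an AE that starts at or after the start of infusion, or that was present before the start of infusion and increases in CTCAE grade after it. Adjust the protocol sentence on pre-dose AEs to match.
2. Use onset time as well as date for events on Day 1. This removes the conflict between the protocol, which counts from the dose, and the SAP, which counts from the dose date.
3. In Protocol 13.2.2 or the eCRF completion instructions, tell the site to record a post-dose grade increase as a new AE record dated at the worsening, so that the definition can be programmed.

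The cost is one sentence in each document, one completion instruction, and an onset time field for Day 1 if the eCRF does not already have one. Slightly more TEAEs may be reported, and event counts rise by one for each worsening. Subject counts in the all-AE tables should not be inflated, because Protocol 14.7 counts a subject once per system organ class and once per preferred term.

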18 DATA HANDLING AND RECORDKEEPING

18.1 Data Collection

All data obtained for analysis in the clinical study described in this protocol will be documented in the eCRF. Data reported in the eCRFs should be consistent with and substantiated by the subject's medical record and original source documents. Any discrepancies must be explained. Unless explicitly allowed in the eCRF instructions, blank data fields are not acceptable. If a field is blank because the item was not done, the field will be marked "Not Done." If the item is unknown, the field will be marked "Unknown."

Prior to the start of the study, the Principal Investigator will complete a Delegation of Authority form (Site Signature and Delegation Log), showing the signatures and handwritten initials of all individuals and the delegation of responsibilities, such as identifying those individuals who are authorized to make or change entries on eCRFs.

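### SAP 6.2 makes every AE with a missing onset date treatment-emergent, with no exception for one reported or ended before the infusion, contrary to Protocol 13.2.1

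*SAP*

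**What the plan says.** SAP 6.2 says that AEs "will be collected from the start of signing the ICF and until 30 days after the administration of the study drug", so events from the screening period, which can last up to 28 days, are in the AE data. It defines treatment-emergent AEs as "events with onset dates on or after the first dose date of the study drug and up to 30 days following the last dose" and places them in incidence tables. For undated events it adds: "Events with missing onset dates will be considered treatment-emergent". It gives no exception based on stop date or time of report, and no rule for partial onset dates.

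Protocol 13.2.1 uses two criteria. One is time of report: "Adverse events reported after consent but before the first dose of study drug are still to be documented by the Investigator". The class that the same sentence assigns to these events is non-treatment-emergent. The other is onset: "Adverse events will be considered treatment-emergent if the onset date is after the first dose of study drug". Neither sentence deals with a missing onset date.

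Protocol 13.2.2 asks the investigator to give the date of onset. Protocol 18.1 has a general eCRF convention for unknown items: "If the item is unknown, the field will be marked 'Unknown". Protocol 14 expects the SAP to set out any changes to the planned analyses, and SAP 9 reports none.

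**The concern.** The two documents classify the same record in opposite ways. Suppose a subject reports a headache at admission on Day -1, it resolves that day, and the onset date is unknown. Under the SAP it is a TEAE; under the protocol it is not. The SAP rule applies even when another recorded fact, such as a stop date before the infusion, proves that the event could not have followed dosing.

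At stake is the TEAE count by treatment. AE and SAE incidence is the first primary endpoint listed in SAP 2.3. Protocol 14.7 plans no formal safety analysis, so the descriptive counts are themselves the result. With six active subjects per dose, a single record can be visible in a column.

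**Working it through.** **Inputs.** Six active and two placebo subjects per cohort, up to four cohorts (Protocol 8.1 and Table 2); placebo pooled in summaries (Protocol 14). This gives 4 × 6 = 24 active and 4 × 2 = 8 placebo subjects, 32 in all, which matches the plan. The documents state no figure for misclassified events, so there is none to reproduce.

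**Step 1: apply each rule to an AE with no onset date.**

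| Reported before dose | Ended before dose | SAP 6.2 | Protocol 13.2.1 |
|---|---|---|---|
| Yes | Yes | TEAE | Not TEAE (time of report) |
| Yes | No | TEAE | Not TEAE (time of report) |
| No | Yes | TEAE | Not TEAE (onset must precede dose) |
| No | No | TEAE | No rule given |

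The documents conflict in the first three rows. In the third row the protocol's report-based sentence does not apply. The conflict there comes from its onset definition, since an event that ended before the infusion must have begun before it. In the fourth row the SAP default fills a gap and is reasonable.

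**Step 2: size of one misclassified subject who has no other TEAE.** The change in overall TEAE incidence is 1/n:
- one dose group: 1/6 = 16.7 points
- pooled placebo: 1/8 = 12.5 points
- all active: 1/24 = 4.2 points
- all subjects: 1/32 = 3.1 points

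If the subject has another TEAE, overall incidence does not move. Only a system organ class or preferred term row in which that subject has no other event would change.

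**Step 3: how often.** The documents give no rate. For an assumed per-subject probability q of a pre-dose AE without an onset date, the chance of at least one affected subject among 32 is 1 − (1 − q)^32:
- q = 0.1%: 3%
- q = 0.5%: 15%
- q = 1%: 28%
- q = 2%: 48%
- q = 5%: 81%

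The spread comes entirely from the assumption. The plan's provisions for recording and querying dates point towards the low end, and the conclusion uses none of these values.

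**Step 4: after the fix.** The first and third rows become non-treatment-emergent from the stop date alone. The second row does so if the date or visit of first report is recorded, or if a known part of the onset date settles it. The fourth row remains a TEAE.

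**The case against.** The best defence is that counting an unknown onset as treatment-emergent is a conservative safety default, that the protocol has no missing-date rule, and that the SAP is meant to add such detail and refers readers back to the protocol. This holds where nothing else dates the event. It does not hold where a report or stop date places the event before dosing: there the rule overrides evidence and contradicts the protocol. Nor is it conservative for every comparison, since a pre-dose event in a placebo subject raises the placebo rate.

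The second defence is rarity. Onset dates are to be specified, blank eCRF fields are not accepted, Protocol 18.3 plans programmed checks and queries, and staff ask about AEs throughout the study. The convention for unknown items is general and not specific to onset dates. All of this stands, and it is the main reason for the low priority.

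The third is limited consequence. All AEs are listed individually with onset, duration and relationship, so a wrong flag could be seen. Some planned summaries cover all AEs, so a pre-dose event may appear in them whatever its flag. This also stands; the point concerns the TEAE incidence tables only.

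A reader might go further and infer that the primary endpoint is materially distorted, that escalation could be affected, or that the SAP discards partial dates. The documents support none of these. The primary endpoint is worded as AEs and SAEs, not TEAEs. The stopping criteria in Protocol 10.6 are not written in terms of the TEAE flag. On partial dates the SAP is silent; it does not say that they are ignored.

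**Conclusion.** The conflict is in the text and does not depend on any assumed rate: for an undated AE that was reported or had ended before the infusion, SAP 6.2 and Protocol 13.2.1 give opposite classes, and SAP 9 does not acknowledge it. The effect is conditional on such a record existing, which should be uncommon. When it does, the shift is 16.7 points in a dose group or 12.5 points in pooled placebo, provided that the subject has no other TEAE; otherwise at most a system organ class or preferred term row changes. No effect on escalation or stopping is shown. Priority: minor.

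**What to change.** Replace the sentence in SAP 6.2 with: *An AE with a missing onset date is considered treatment-emergent unless its stop date, any known part of its onset date, or (where recorded in the eCRF or source) the date or visit at which it was first reported shows that it began before the start of infusion.* This keeps the conservative default where timing is truly unknown. If the sponsor prefers the unconditional rule, SAP 9 should declare it as a departure from Protocol 13.2.1.

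The cost is one extra condition in the AE derivation, to be settled before unblinding. A stop date should be available, since the planned AE listing includes duration. A date or visit of first report is not among the AE items named in Protocol 13.2.2 or SAP 6.2, so that part of the rule can be applied only if it is in fact recorded. For an undated event reported before dosing and still ongoing, it may be the only information that can settle the class.
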